- o Participants must adhere to proper stool incubation requirements and return stool to site within 24 hours of producing sample. AMAG and AMAM participants dispensed pre-endoscopy stool collection kit per SoA. AMAG participants should also receive stool collection kit at the visit prior to the endoscopy performed at CCI [REDACTED]. Instruct participants to collect stool samples up to 3 days prior to beginning bowel prep for endoscopy. For stool collection for testing associated with other visits, the sample collection kits may be sent home in earlier visits. This allows the participants to collect samples within 24 hours prior to their visit and bring to the site on the day of visit. If samples are not collected before or on the day of the visit, the collection kit should be sent home with the participant on the day of the visit, and sample should be collected as soon as possible and returned to the site within 24 hours of producing the sample. For AMAG-originating participants at V1, the collection may be performed at the first day of screening and must be collected prior to dosing.
- p Visits will differ for participant collections via paper diary or electronic diary capture. See Section 8.1.2.2 for instructions.
- q Dispensed at V1a to AMAM participants only. Includes CCI [REDACTED] CDAI-SF with Bristol Stool Scale, CDAI-AP, CDAI well-being, CCI [REDACTED] [REDACTED] (See Section 8.1.2.2).

- r Collected only from AMAM participants.
- s The CCI [REDACTED] endoscopy should be performed for AMAG-originating participants CCI [REDACTED] (See [Table AMAX.1-3](#)) and is notated here under V1 only as a reminder, since it could occur over a wide window of time within the AMAX schedule. At the visit prior to the CCI [REDACTED] endoscopy, the site should provide the participant with one 14-Day paper diary to be returned at the next regularly scheduled office visit. The 14-Day diary should be completed in the 14 days leading up to the next regularly scheduled office visit and may begin before or after the endoscopy, depending on endoscopy timing (See [Table AMAX.1-3](#))
- t The 14-Day paper diaries and 1-Day paper diaries both include: CCI [REDACTED] CDAI-SF with Bristol Stool Scale, CDAI-AP, CDAI well-being, CCI [REDACTED] (See Section [8.1.2.2](#)).
- u Collections required only for participants from AMAM. Collect at AMAX V1a if data were not collected at the final visit in the originator study.

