- m Participants previously testing HBcAb+ do not need to be retested for HBV serology (Section 8.2.8).
- n Perform at ETV only if participant had ongoing monitoring for HBV DNA previously or was found to be HBcAb+ by the time of the ETV. Any enrolled participant who is HBcAb+ and meets the requirements to continue in the study as described in Section 8.2.8 will undergo monitoring of HBV DNA at specified intervals. Any participant not meeting the requirements to continue in the study at any time must be discontinued from the study and receive appropriate follow-up medical care (Section 8.2.8).
- o Samples will be collected predose per the SoA. Additionally, in the event of a systemic allergic/hypersensitivity event (Section 6.7), blood samples will be collected for PK, ADA, CCI [REDACTED] at the following time points: as close as possible to: (1) the onset of the systemic allergic/hypersensitivity event, (2) the resolution of the systemic allergic/hypersensitivity event, CCI [REDACTED] [REDACTED]

p In the event of a systemic allergic/hypersensitivity event, blood samples will be collected for PK, ADA, CCI [REDACTED] at the following time points: as close as possible to: (1) the onset of the systemic allergic/hypersensitivity event, (2) the resolution of the systemic allergic/hypersensitivity event, CCI [REDACTED]

q CCI [REDACTED]

r Participants must adhere to proper stool incubation requirements and return stool to site within 24 hours of producing sample. AMAG-originating participants should receive stool collection kits in AMAX at the visit CCI [REDACTED] Instruct participants to collect stool samples CCI [REDACTED]. Fecal calprotectin is only tested at the CCI [REDACTED] office visit does not coincide with a regularly scheduled visit that already collects this lab. For stool collection at the ETV and at optional timepoints, the sample collection kits may be sent home in earlier visits. This allows the participants to collect the samples within 24 hours prior to their visit and bring to the site on the day of visit. If samples are not collected before or on the day of the visit, the collection kit should be sent home with the participant on the day of the visit, and sample should be collected as soon as possible and returned to the site within 24 hours of producing the sample.

s Visits will differ for participant collections via paper or electronic diary capture (Section 8.1.2.2).

t Collected from AMAM participants only.

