u Return of the 14-Day paper diary only applies for the ETV if participant has a pending diary return. At the visit prior to CCI [REDACTED], the site should provide the participant with one 14-Day paper diary to be collected at the next regularly scheduled office visit (also see Footnote b).

v The 14-Day paper diaries and 1-Day paper diaries both include: CCI [REDACTED] CDAI-SF with Bristol Stool Scale, CDAI-AP, CDAI well-being, CCI [REDACTED] (See Section 8.1.2.2.).

w CCI [REDACTED], as indicated in the table. For each visit with an endoscopy, it is recommended that the endoscopy be performed on a separate day from the vital signs and study questionnaires, and IP administration, within the visit window, with the endoscopy preceding the other activities. However, if they must be performed on the same day due to logistical issues, the following period order of procedures must be followed: (1) Measurement of vital signs and collection of responses to questionnaires; (2) Administration of IP with protocol-specific observation (at least 1 hour); (3) Performance of endoscopy with or without sedation. An ETV endoscopy should only be performed if the ETV occurs at least 16 weeks after the last endoscopy. An ETV endoscopy will not be performed during the follow-up period.

x Participant to return the *Patient Study Drug Administration Log* at the next visit.

y Participants who are eligible for continued access should move directly from Visit 19 to Visit 501, on the same day, if possible. Visit 801 and Visit 802 should not be performed for these participants.

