6.4. Study Intervention Compliance

Detailed instructions for investigational product administration, including infusion rate and SC injections, will be provided separately by the sponsor.

Every attempt will be made to select participants who have the ability to understand and comply with study instructions. The investigator is responsible for discussing methods to ensure high treatment compliance with the participant.

In particular, the investigator is responsible for ensuring that study participants receive adequate training on and appropriate understanding of

- the importance of complete bowel prep prior to colonoscopies
- how to evaluate their CD symptoms and to record them on the eDiary, paper diary, or questionnaires.
- the importance of being compliant with the daily eDiary or paper diary recording, and
- SC self-administration by the participant or caregiver.

If a participant is noncompliant with study procedures and/or investigational product administration, the investigator should assess the participant to determine the reason for noncompliance and educate and/or manage the participant, as appropriate, to improve compliance.

If, in consultation with Lilly or its designee, the noncompliance is deemed to be significant or if further noncompliance occurs, the participant may be discontinued. See Section [7.1.2](#) for treatment noncompliance leading to permanent discontinuation from study drug.

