- Timeframes for future participant visits and self-administration of dosing, where applicable, must be adjusted to bring the participant back into compliance with the protocol defined visit windows, while keeping all doses at least CCI apart.

Throughout trial

- A urine pregnancy test (if applicable) must be obtained prior to each IP administration.
- If a 14-Day paper diary is in use and the subsequent visit is delayed, the participant should continue to record the daily data, even beyond 14 days, until the next visit occurs (guidance will be provided for ensuring sufficient forms are available).
- Note: Per protocol, participants who miss CCI must be considered for ET.

Endoscopies

- For CCI, the window for the CCI If the CCI cannot be performed within the extended window, the CCI should be performed as soon as possible.
- For CCI, if the AMAX Week 52 CCI endoscopy cannot be performed within the extended V9 window, the site should still perform all other assessments and may continue with dosing. The Week 52 endoscopy should be performed as soon as possible. At the time of the endoscopy, an unscheduled fecal-calprotectin stool sample should be collected.
- If the CCI endoscopy cannot be performed within the extended CCI window, the site should still perform all other assessments. The CCI should be performed as soon as possible. At the time of the endoscopy, an unscheduled fecal-calprotectin stool sample should be collected.

- The overall length of exposure will not be extended for this trial.

Posttreatment Follow-Up Visits 801 and 802

- Visit 801: Visit window may be extended up to 2 weeks earlier or less than 12 weeks from the last visit (LV) or ETV (LV/ETV + 2 weeks to <12 weeks).
- Visit 802: Visit window may be extended up to 4 weeks earlier (provided Visit 802 is at least 4 weeks from Visit 801) or 8 weeks later than the protocol visit date (LV/ETV + 8 weeks to 24 weeks). If additional time is required, a discussion with the sponsor should take place.

Documentation

Changes to study conduct will be documented:

- Sites will identify and document the details of how participants, visits, and conducted activities were affected by exceptional circumstances. Dispensing/shipment records of study intervention and relevant communications, including delegation, should be filed with site study records.

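### Appendix 12 ties the calprotectin sample for a delayed endoscopy to the procedure itself, against the protocol's own rule of collecting stool before bowel prep; the ETV footnote leaves a similar gap

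*Protocol*

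**What the plan says.** **Scheduled endoscopies.** SoA footnote o to Table AMAX.1-1 says "Instruct participants to collect stool samples up to 3 days prior to beginning bowel prep for endoscopy", and footnote j to Table AMAX.1-2 gives the same instruction. Footnote o also says "AMAG and AMAM participants dispensed pre-endoscopy stool collection kit per SoA". In both footnotes, collection in the 24 hours before the visit is offered only for stool tests tied to other visits.

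**Delayed endoscopies.** Protocol Appendix 12 (Section 10.12, Endoscopies) covers an endoscopy that cannot be done within the extended window. One bullet concerns Week 52 and another a time point that is redacted. Both end: "At the time of the endoscopy, an unscheduled fecal-calprotectin stool sample should be collected". The Visit 19 office row of Table AMAX.10-1 repeats the instruction for Week 156. None of the three mentions bowel prep.

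**Early termination.** Footnote r to Table AMAX.1-3 says "For stool collection at the ETV and at optional timepoints, the sample collection kits may be sent home in earlier visits", so that participants can "collect the samples within 24 hours prior to their visit and bring to the site on the day of visit". It continues: "If samples are not collected before or on the day of the visit, the collection kit should be sent home with the participant". Footnote w says "An ETV endoscopy should only be performed if the ETV occurs at least 16 weeks after the last endoscopy".

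**SAP.** Appendix 1 treats fecal calprotectin as a single laboratory result and has no rule on its timing relative to prep. Appendix 2 summarises it at every visit with a measurement.

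**The concern.** The SoA separates stool collected for an endoscopy, which must precede prep, from stool collected for other visits, which may be taken within a day of the visit. That distinction looks deliberate. Appendix 12 drops it where an endoscopy has been delayed, and footnote r does not visibly keep it where an ETV includes one.

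At stake is comparability. Some calprotectin values would come from stool taken before prep and others from stool taken during or after it, with nothing in the data to tell them apart. Appendix 12 also says that the changes it describes are not protocol deviations, so a site that follows the literal wording leaves no deviation record to show the timing.

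**Working it through.** No arithmetic applies. The check sets the timing rules side by side and follows each case through to the analysis.

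**Order of events.** Protocol Section 6.4 makes investigators responsible for training participants on "the importance of complete bowel prep prior to colonoscopies". Prep therefore starts before the procedure.

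**Collection timing**

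| Case | Instruction | Position relative to prep |
|---|---|---|
| Scheduled endoscopy (footnotes o, j) | Up to 3 days before prep begins | Before |
| Delayed endoscopy (Appendix 12, two bullets; Visit 19 note) | When the endoscopy takes place | After prep has begun, read literally |
| ETV with same-day endoscopy (footnote r) | Within 24 hours before the visit, on the day, or later | Can overlap or follow prep |
| ETV with endoscopy on an earlier day (footnotes r, w) | Same | Can follow prep, procedure and biopsies |
| ETV without endoscopy | Same | No prep, no conflict |

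The second row conflicts with the first. In the third and fourth rows a post-prep sample is possible but not required, because footnote r is permissive. Two redactions limit what can be shown for the ETV. The sentence in footnote r that corresponds to the pre-prep instruction has its timing blacked out. The label of the stool row marked for the ETV in Table AMAX.1-3 is also blacked out, so that calprotectin is the assay there is an inference.

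**Where the values go**

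- *Scheduled sample.* When the Week 52 or Week 156 endoscopy is delayed, Appendix 12 still has the site complete the other assessments. The regular Visit 9 or Visit 19 sample therefore remains, and the questionable one is additional.
- *Secondary endpoint.* The visible calprotectin endpoint is at Week 12 (Protocol Section 3) and is listed for participants from Study AMAM. Their first visible scheduled endoscopy in AMAX is at Week 52 (Protocol Section 4.1).
- *Main continuous analysis.* SAP Section 5.1.5 uses ANCOVA with modified baseline observation carried forward. After discontinuation for most reasons, values return to baseline. After discontinuation for commercial availability or extraordinary circumstances, participants leave the analysis at later time points.
- *MMRM sensitivity analysis.* SAP Section 5.1.1 excludes early-discontinuation data that fall off the planned collection schedule.
- *As-observed summaries.* These use whatever value is recorded. SAP Appendix 1 does not say how an unscheduled or ETV calprotectin result is assigned to a visit.

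**Contrast within the SAP.** Appendix 9 drops diary entries for the prep days, the procedure day and the two days after it. Calprotectin has no matching rule.

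**The case against.** The strongest reply concerns Appendix 12. Its phrase may mean only that the extra sample goes with the delayed endoscopy instead of the missed visit date. The pre-prep instruction is attached to prep for endoscopy, Appendix 12 does not withdraw it, and the appendix asks sites to keep to the usual SoA where they can. A careful site could comply with both. That reading is reasonable, but the text does not secure it. Appendix 12 neither mentions prep nor points back to footnotes o and j. It calls the sample unscheduled, and footnote r places optional time points under the 24-hour or take-home route.

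The ETV part is weaker, and the objections to it largely stand. The rule is permissive and partly redacted. The activities that footnote w places after the endoscopy are vital signs, questionnaires and dosing; stool collection is not named.

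It is also fair to say that the documents give no effect of bowel prep on calprotectin and plan no visible analysis pairing it with the endoscopic score. The SAP accepts a Week 52 endoscopy only up to 14 days after the visit and before further dosing, whereas Appendix 12 lets dosing continue. Some delayed endoscopies would therefore not supply a Week 52 score at all.

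**Conclusion.** The conflict between Appendix 12 (with the Visit 19 note) and SoA footnotes o and j is real on the literal wording and should be reconciled. For the ETV, the finding is a gap: nothing visible prevents a sample during or after prep when the visit includes an endoscopy. This rests on the unredacted text, on prep preceding the procedure, and on calprotectin being the ETV stool assay.

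The consequence is small. It falls mainly on the extra delayed-endoscopy samples and on as-observed summaries.

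A reader might infer that every delayed-endoscopy and ETV sample is invalid, or that early terminators bias the calprotectin results. The documents do not support either. Collection before prep remains possible under footnote r and under the softer reading of Appendix 12. No passage says that prep invalidates the specimen; this can only be inferred from the pre-prep rule. The main and sensitivity analyses give ETV values little or no role. The documents contain no figure from which to count affected samples.

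**What to change.** 1. In both Appendix 12 bullets and the Visit 19 note of Table AMAX.10-1, replace the timing phrase with: *before bowel preparation for the delayed endoscopy begins (up to 3 days prior, as in SoA footnotes o and j)*.
2. In footnote r, state that when the ETV includes an endoscopy, the stool is collected before bowel prep where possible.
3. Record the collection time relative to the start of prep.
4. In the SAP, flag any calprotectin sample taken during or after prep, or exclude it from the summaries, in line with the existing treatment of diary days around the procedure.

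The cost is wording in one appendix, one table note and one footnote, one timing item to record, and one SAP rule. Kit and assay stay the same. The downside is that a few ETV or delayed-endoscopy values may be excluded.

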10.13. Appendix 13: Optional Continued Access Period

10.13.1. Overview

This appendix will provide optional continued access to open-label mirikizumab for eligible patients following the completion of the long-term extension period of AMAX.

The duration of the Continued Access Period will differ by participant and country.

Efficacy data will not be collected during the Continued Access Period. Participants will continue to be followed for safety throughout their participation in this Continued Access Period.

CCI

CCI

10.13.3. Schedule of Activities for Continued Access Period

Throughout this appendix, “self-administration” refers to injection of mirikizumab by the participant or caregiver.

All visits

Office visits will generally occur every **CCI**. Self-administration of mirikizumab **CCI** is required, regardless if the dosing is onsite or remote (refer to Section 10.13.7 for more detail). All other visit activities should be completed prior to self-administration of mirikizumab, unless otherwise stated below.

Continued Access Treatment (Visit 501 to last dosing visit)

Visit 501 activities should occur on the same day as Visit 19 of the long-term extension period if possible. It is recommended that the Visit 19 endoscopy be performed first, on a prior date within the Visit 19 window, followed by a combined Visit 19/ Visit 501 office visit on a later day also within the Visit 19 window.

If this is not possible, the Visit 19 endoscopy can be performed on the same day as the Visit 19 office visit, with Visit 501 being performed on a later date within window. Ensure all Visit 19 activities are completed prior to starting Visit 501 activities and dosing.

If Visit 19 and Visit 501 do not occur on same day, Visit 501 activities may need to be repeated, as detailed in the continued access period SoA.

If Visit 19 and Visit 501 occur more than 2 weeks apart, the following laboratory tests must be repeated: hematology, clinical chemistry, and HBV DNA.

Extended continued access visits (ECAV)

After Visit 502 (**CCI**), ECAV continue until criteria for the final visit occurs (outlined in Section 10.13.8).

Onsite ECAV Visits occur every **CCI**

Visit numbers will be registered sequentially after Visit 502. This table provides an example of the ECAV visit structure that will continue until the final visit.

Visit Number	Visit ID	Weeks from AMAX Visit 1
502	502	
ECAV	503	CCI
ECAV	504	
ECAV	505, 506, 507...	ECAV will continue until criteria for final visit occurs

Discontinuation (DC) visit

All participants who discontinue mirikizumab treatment after Visit 501 should complete this DC Visit.

Continued Access Period follow-up (4 weeks)**Visit 901**

All participants will complete this visit following their DC visit or at the end of their participation in the Continued Access Period of the study.

V901 may be performed onsite when onsite activities are required or at investigator's discretion.

Unscheduled visits

Unscheduled visits may occur as needed, on any day without regard to visit interval. Required activities are indicated in the SoA. Additional procedures may be performed at the investigator's discretion.

Procedures		AMAX Continued Access Period Schedule of Activities ^a					
Visit Number	501	502	ECAV	DC	UV	V901	
Visit Type	Office	Office	Office	Office	Office	Phone	
Week Relative to Study Drug Start ^b	CCI						
Visit Tolerance Interval (VTI) in days							
All Participants (X); Optional (Opt) (See footnotes for additional key details)							
Confirmation of Informed consent	X						
Inclusion and exclusion criteria	X						
Concomitant medications	X ^c	X	X	X	X	X	X
Tobacco/Nicotine use				X ^d			
AEs ^e (See Section 8.3)	X ^c	X	X	X	X	X	X
Physical Evaluation							
Vital signs (T, PR, BP) (See Section 8.2.1)	X ^c	X	X	X	X	X	
Weight	X ^c	X	X	X	X	X	
Physical examination ^f (See Section 8.2.2)	X ^c	X	X	X	X	X	
TB Risk Assessment Monitoring ^g	X ^c	X	X	X	X		
Participant Education							
Self-administration retraining		Opt ^h				Opt ^h	
Laboratory Tests							
Chemistry	X ⁱ	X	X	Opt	Opt		
Hematology	X ⁱ	X	X	Opt	Opt		
Urine pregnancy (local) ^j (See Section 8.2.7.1)	X ^c	X	X	X			X
HBV DNA monitoring ^k	X ⁱ	X	X	X			
Hypersensitivity kit (tryptase, PK, and immunogenicity)		X ^l					
On-Site Questionnaires (Paper)							
QIDS-SR16			X ^m	X	Opt		
CCI							

Procedures		AMAX Continued Access Period Schedule of Activities ^a				
Visit Number	501	502	ECAV	DC	UV	V901
Visit Type	Office	Office	Office	Office	Office	Phone
Week Relative to Study Drug Start ^b	CCI					
Visit Tolerance Interval (VTI) in days	CCI					

CCII

CXR = chest x-ray; DC = discontinue; ECAV = extended continued access visits, FSH = follicle-stimulating hormone; HBcAb = hepatitis B core antibody; HBV = hepatitis B virus; IGRA = interferon gamma release assay; IP = investigational product; IWRS = Interactive Web Response Systems; PK = pharmacokinetic; PR = pulse rate; CCI (); SoA = schedule of activities; T = temperature; TB = tuberculosis; TST = tuberculin skin test; UV = unscheduled visit; V = visit.

- a Please see detailed instructions provided by the sponsor for calculation of visit dates. Additional AMAX SoA procedures may be performed during Continued Access at other timepoints at the investigator's discretion (for example HBV DNA monitoring, urine pregnancy tests, TB Risk Assessment Monitoring, or others). Please contact your monitor for questions.
- b All activities should be completed prior to any study drug administration unless otherwise stated. ECAV visits will occur every **CCI** until patient meets discontinuation criteria.
- c If visits 501 and V19 do not occur on the same day, these activities must be repeated
- d Tobacco/Nicotine use data will be collected yearly.
- e For AESIs, additional data are collected (See Section [8.3.7](#)).
- f Includes a symptom-directed evaluation as well as examination of eyes, heart, lungs, abdomen, and visual examination of the skin (Section [8.2.2](#)).
- g Throughout the study, participants will be assessed for risk factors for TB (Section [10.5](#), Appendix 5). If the participant has a risk factor(s) or any TB-related signs or symptoms identified as part of the discussions of AEs or as part of the standard physical exam, the investigator should conduct a thorough exam to evaluate for TB, including examination of peripheral lymph nodes and documentation of body temperature. If there are relevant physical findings or other factors that the investigator feels warrant testing and imaging, an IGRA or TST and CXR should be performed (Table [AMAX.1-3](#) Unscheduled assessments). A CT scan can be performed as an alternative to the CXR based on regional standard of practice (Section [8.2.6](#)).

- h Complete at the investigator's discretion. See Section 10.13.7.
- i If there are not results available from safety laboratory collections within CCI of Visit 501, these laboratory tests must be repeated and results reviewed prior to dosing.
- j To be performed only on women of child-bearing potential. Done locally and prior to dosing (Section 8.2.7.1). Between visits, urine pregnancy tests are to be performed prior to monthly at-home dosing. Optional FSH may be performed as needed to confirm postmenopausal status in female participants. See Section 5.1
- k Perform only if participant had ongoing monitoring for HBV DNA during the long-term extension period of Study AMAX, or for participants in the Continued Access period who were found to be HBcAb+ and meet the requirements to continue in the study as described in Section 8.2.8. Such participants will undergo monitoring of HBV DNA at specified intervals. Any participant not meeting the requirements to continue in the study at any time must be discontinued from the study and receive appropriate follow-up medical care (Section 8.2.8).
- l In the event of a systemic allergic/hypersensitivity event, blood samples will be collected for PK, ADA, CCI at the following time points: as close as possible to: (1) the onset of the systemic allergic/hypersensitivity event, (2) the resolution of the systemic allergic/hypersensitivity event, CCI
- m CCI to be administered every 6 months during continued access period.
- n Visit procedures and assessments must be completed prior to dosing.
- o Dispense study drug at each office visit CCI Changes cannot be made to dispensing and planned office visit schedules without prior sponsor approval (and potentially changes to safety lab testing schedule). Continue to dispense ancillary supplies at each visit as needed. Note that any used or unused study drug may be returned as an optional unscheduled activity at subsequent visits (see Table AMAX.1-3).
- p Site to complete and dispense *Patient Study Drug Administration Log*. Provide syringes for next dosing, inform participant of dosing date for self-injection, and provide ancillary supplies to participant.
- q Participant to return the *Patient Study Drug Administration Log* at the next visit.

